## Protocol Summary

This is a randomized, open-label clinical investigation of the effects of short-term oral metformin therapy on biomarkers for tumor growth in subjects with endometrial cancer. Metformin is a well-tolerated drug widely prescribed for treatment of Type 2 diabetes mellitus and for treatment of Polycystic Ovarian Syndrome (PCOS) in non-diabetic women. Clinical trials are ongoing to explore this possibility in breast cancer (NCT01101438). This investigation is the first study of metformin in endometrial cancer patients, and is designed to understand the mechanism of its anti-cancer actions, if any, and its interactions with biomarkers in endometrial cancer patients.

Forty non-diabetic subjects will be randomized so that 20 will receive oral metformin for 14-21 days and the remaining 20 will receive no metformin for 14-21 days. Subjects will be monitored for adverse events (AEs). All subjects will have blood samples collected on Day 1 (prior to start of metformin for subjects randomized to metformin) and prior to surgery. These samples will undergo metabolic, lipid and tumor-specific biomarker analyses. Tumor and adjacent normal tissue taken from subjects from the diagnosis and at the time of surgery will be analyzed for cellular proliferation, apoptosis and biomarker levels.

The **Primary objectives** of this study are as follows:

1. To determine the effect of metformin on tissue markers of proliferation, apoptosis, and insulin-mediated signaling in endometrial cancer in non-diabetic obese women.
2. To determine the tolerability of a short course of metformin in non-diabetic obese women with newly diagnosed endometrial cancer.

The **Secondary objectives** of this study are as follows:

1. To determine the effect of metformin on HbA1c and blood lipid profiles measured at baseline and just before surgery.
2. To determine the effect of metformin on the following hormones measured in blood plasma at baseline and just before surgery: Insulin, IGF-I, leptin, and adiponectin.
3. To determine the effect of metformin on the expression levels of mRNAs and miRs measured in blood plasma at baseline and just before surgery.
4. To determine the effect of metformin on the expression levels of mRNAs and miRs measured in tumor and adjacent non-tumoral uterine tissue.

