## Proliferation Markers

Human endometrial cancer cell lines ECC-1 and Ishikawa, when treated with metformin, showed decreased proliferation and decreased hTERT expression relative to non-treated cells. In women treated with metformin to manage PCOS, sera from PCOS women after 6 months of metformin significantly decreased the invasive properties of ECC-1, in part, by attenuating pro-inflammatory NF- $\kappa$ B expression and activation of Akt and Erk1/2 pathways. Further, the increase in progesterone receptor expression in metformin-treated Ishikawa and HEC-1B cells was associated with pathways targeted by adipokines and insulin.

In this pilot study, we will evaluate the effect of metformin on endometrial tumor-cell proliferation and apoptosis, obesogenic and pro-tumorigenic marker gene expression, and anti-oncogenic micro-RNA (miR) expression. miRs are potentially important regulators of expression of tumor-enhancing and tumor-suppressing pathway components. Endometrial tumors and adjacent non-involved tissues will be obtained at surgery. Tissues will be processed for histopathology and immunohistochemistry, and frozen in liquid nitrogen for RNA and protein analyses. Fasting blood sera will be obtained prior to and after the 14-to-21-day treatment period for measurement of insulin, adiponectin, leptin, and IGF-1 levels. Fixed tumor and 'normal' tissues will be analyzed for markers of proliferation (Ki67; phospho-histone H3) and apoptosis (TUNEL), and for expression of estrogen receptor (ER) $\alpha$ , progesterone receptor (PR), and tumor suppressor PTEN by immunohistochemistry. Isolated tissue RNAs will be assessed for PR, PTEN, ER $\alpha$ , KRAS, and hTERT transcripts by quantitative RT-PCR. Protein extracts will be evaluated by Western immunoblotting for PR, PTEN, total and activated Akt and Erk 1/2, and insulin receptor expression. Sera from both groups at both time points will also be subjected to analysis using miR-profiling arrays. Data obtained from analyses of all biological endpoints will be compared using standard statistical procedures.

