**B. Blood Draws and Laboratory Tests**

Blood will be drawn from each subject, approximately 18 mL in purple top vacutainers, prior to treatment assignment (if not preformed previously as conventional care) and after completion of the therapy at the time of surgery. The blood sample below will be subjected to the following tests at the UAMS Clinical Laboratory:

- a) A comprehensive metabolic panel (glucose, calcium, albumin, total protein, sodium, potassium, CO2, chloride, BUN, creatinine, ALP, ALT, AST and total bilirubin), to be performed prior to starting treatment only.
- b) A lipid panel (cholesterol, HDL-C, LDL-C, triglycerides), to be performed both prior to treatment assignment and at the time of surgery.
- c) Determination of HbA1c, to be performed both prior to treatment assignment and at the time of surgery.

The blood samples listed below will be utilized for correlative laboratory studies in the research laboratory of [name] at the UAMS Biomed Bldg. Aliquots of each blood sample will be centrifuged to separate out the plasma portion. Plasma will be stored at -80°C in the Co-Investigator's lab until analysis is performed.

The following biomarkers will be assayed in the plasma samples collected at baseline and at the time of surgery through enzyme-linked immunosorbent assays (ELISA) or multiplex assays. All of these tests will be performed by laboratory personnel in [name] lab:

- a) Insulin
- b) Leptin
- c) Adiponectin
- d) IGF-I and IGF-II

Remaining plasma samples will be subjected to global profiling of miRs and mRNAs to evaluate/validate the relative expression of specific candidate metformin-regulated miRs and mRNAs ([name] lab). miR and mRNA levels will be determined using quantitative SYBR green-based real time reverse transcriptase polymerase chain reaction (RT-PCR) assays and a microarray platform. These tests will be performed in [name] laboratory by his personnel and/or by commercial providers of microarray profiling services.

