### **C. Tissue Specimens and Laboratory Tests**

A sample of tumor with adjacent normal mucosa will be obtained after surgery from the Pathology department from the tissue remaining after normal gross and histological assessments.

Fresh tissue samples will be transported by designated research personnel to [name] laboratory at the UAMS Biomed Bldg. Fixed tumor and 'normal' tissues will be subjected to IHC for markers of proliferation (*Ki-67*, phospho-histone H3), and apoptosis (TUNEL, cleaved caspase-3). Tumor (and 'normal') tissues will also be examined by Western blot and/or ELISA for expression levels of FASN, total and phosphorylated insulin receptors, and total and phosphorylated IGF-I receptors. Total and phosphorylated AMPK levels will be assessed by IHC or Western blot. Lastly, tissues will be used for miR and mRNA profiling.

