## Statistical Considerations

General approach: For each tissue endpoint, the tumor-NTU difference will be calculated in each patient as the paired difference in values between tumor and adjacent NTU tissue. For each blood endpoint, the endpoint response to treatment will be calculated in each patient as the paired difference between post-study and pre-study values. All data will be summarized by treatment arm as the mean, standard deviation (SD), median, and range, and will be graphed as box plots. Tumor-NTU differences and endpoint responses will be compared against zero via signed-rank test within each treatment arm. Treatment arms will be compared to each other for differences via Wilcoxon rank-sum tests, with additional details provided below. All statistical comparisons will be two-sided, and will employ a 10% alpha to reduce Type II error in this pilot proof-of-concept study.

Analysis plan for tolerability: Meformin-related adverse events will be summarized by type and treatment arm, both as proportions at each grade and as average grades (i.e., mean scores). For each type, the Wilcoxon rank-sum test will be used to compare treatment arms for differences in average grade.

Analysis plan for the IHC-based primary endpoints: The IHC-based primary endpoints will be measured in tissue, and will include markers of proliferation (Ki67, phospho-histone H3, ER $\alpha$ , PR, and hTERT), anti-proliferation and apoptosis (PTEN, KLF9, cleaved caspase-3 and TUNEL staining), and insulin-mediated signalling (total and phosphorylated versions of Akt, Erk1/2, AMPK, and receptors for Insulin, IGF-I, and IGF-

II). Endpoints measured in tumor tissue, adjacent NTU tissue, and tumor-NTU differences will be summarized and graphed as described above. Wilcoxon rank-sum tests will be used to compare endpoints measured in tumor, and likewise endpoints measured in adjacent NTU tissue, for differences between the metformin and no-metformin treatment arms.

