Analysis plan for secondary endpoints measured in blood or plasma: The secondary endpoints measured in blood will be the levels of HbA1c, cholesterol, HDL-C, LDL-C, and triglycerides. The secondary endpoints measured in plasma will be the plasma hormone levels (Insulin, IGF-I, IGF-II, leptin, and adiponectin) and the plasma-measured expression levels of mRNAs and miRs. Endpoints measured at pre-study and post-study, and endpoint responses to treatment will be summarized and graphed as described above. Wilcoxon rank-sum tests will be used to compare endpoint responses to treatment for differences between the metformin and no-metformin treatment arms.

Analysis plan for secondary endpoints measured in tissue: The secondary endpoints measured in tissue will be the expression levels of mRNAs and miRs. Endpoints measured in tumor tissue, adjacent NTU tissue, and tumor-NTU differences will be summarized and graphed as described above. Wilcoxon rank-sum tests will be used to compare endpoints measured in tumor, and likewise endpoints measured in adjacent NTU tissue, for differences between the metformin and no-metformin treatment arms.

Sample Size and Power: There will be 20 subjects on each treatment arm, yielding a total of 40 subjects. The two-sided Wilcoxon rank-sum test will be used at 10% alpha to compare all endpoints and endpoint responses for differences between the metformin arm and the no-metformin arm. This study will be considered sufficiently powered to meet research objectives if the Wilcoxon rank-sum test has >90% power at 10% alpha to detect a treatment-arm difference of 1.0 SDs or more. Statistical power of the Wilcoxon rank-sum test was calculated using the 2-sample t-test module of PASS 2011 by selecting options corresponding to the worst-case scenario of underlying normal distributions with unknown SDs. Under this worst case scenario, 20 subjects per treatment arm (for a total of 40 subjects) give the two-sided Wilcoxon rank-sum test 91.6% power at 10% alpha to detect a difference of 1.0 SDs between the metformin and no-metformin arms, thereby establishing that this study is sufficiently powered to meet research objectives.

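### Ten blood analytes have a scheduled baseline that enters the arm comparison only as a raw change: a valid test that may give up precision

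*Protocol*

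**What the plan says.** Statistical Considerations in the Protocol, repeated in the SAP, defines the blood response as a simple difference: "For each blood endpoint, the endpoint response to treatment will be calculated in each patient as the paired difference between post-study and pre-study values". For the secondary endpoints in blood or plasma, the between-arm test is then: "Wilcoxon rank-sum tests will be used to compare endpoint responses to treatment for differences between the metformin and no-metformin treatment arms". No comparison that adjusts for the pre-study value is planned for any analyte.

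The baseline is scheduled. Section B (Blood Draws and Laboratory Tests) has HbA1c and the lipid panel measured before assignment and again at surgery. For the hormones it says: "The following biomarkers will be assayed in the plasma samples collected at baseline and at the time of surgery". The Study Calendar agrees. The Protocol Summary places the first research sample before metformin starts, so on any of these readings the value precedes treatment and is a legitimate covariate.

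The Sample Size and Power paragraph says the rank-sum test will be used to "compare all endpoints and endpoint responses for differences between the metformin arm and the no-metformin arm". It sets a criterion of more than 90% power for a 1.0 SD difference, without saying whether the SD is that of the level or of the change.

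On tissue, the between-arm test names no time point: "Wilcoxon rank-sum tests will be used to compare endpoints measured in tumor, and likewise endpoints measured in adjacent NTU tissue". The Protocol Summary includes both specimens: "Tumor and adjacent normal tissue taken from subjects from the diagnosis and at the time of surgery will be analyzed for cellular proliferation". Proliferation Markers says "Endometrial tumors and adjacent non-involved tissues will be obtained at surgery", and section C says "A sample of tumor with adjacent normal mucosa will be obtained after surgery from the Pathology department". Neither mentions a diagnostic specimen. The Study Calendar lists pre-study tissue, subject to availability.

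**The concern.** When the two measurements are only weakly or moderately correlated, subtracting the full baseline adds its noise to the outcome. Below r = 0.5 the change is even more variable than the surgery value alone. Regression on the baseline removes only the part that predicts the surgery value, so in large samples it does at least as well as subtraction on a scale where the relation is linear.

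With 20 patients per arm this can matter for the ten blood comparisons, and the baseline needed is already being collected. What is at stake is precision on secondary endpoints. Bias and type I error are not in question.

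**Working it through.** **Inputs from the documents.** 20 per arm; two-sided 10% alpha; rank-sum test; 1.0 SD difference; stated power 91.6%; ten named analytes (HbA1c 1 + lipids 4 + hormones 5).

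**Assumptions, not in the documents.** Correlation r between the pre-study and surgery values, taken over 0.3 to 0.95; equal SDs at the two visits; normal data unless stated.

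**Step 1: the plan's own figure.** The rank-sum test has efficiency 3/π against the t-test under normality, so the effective size is 20 × 0.955 = 19.1 per arm. Two-sample noncentral-t power with noncentrality d√(n/2) and d = 1 is 91.7% at n = 19.1 and 91.6% at n = 19. The stated 91.6% reproduces.

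**Step 2: efficiency of the change.** In units of the level SD:
- variance of the change: 2(1 − r)
- variance after linear baseline adjustment: 1 − r² = (1 − r)(1 + r)
- efficiency of the change: (1 − r²) / [2(1 − r)] = (1 + r)/2

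Multiplying by 20 gives the number per arm that an adjusted analysis would need for the same precision: 20 × 0.65 = 13, 20 × 0.75 = 15, 20 × 0.85 = 17, 20 × 0.95 = 19.

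**Step 3: power by simulation.** At least 40,000 replicates per setting, exact rank-sum critical value (attained size 9.65%). Each power cell is rank-sum on the change versus rank-sum on pooled-arm residuals. The SD of the change is √(2(1 − r)) level SDs, so the two effect scales coincide at r = 0.5.

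| r | Efficiency of change | Adjusted n per arm doing the same work | Power, effect 1.0 level SD | Power, effect 1.0 SD of change |
|---|---|---|---|---|
| 0.3 | 65% | 13 | 82 vs 93% | 91 vs 98% |
| 0.5 | 75% | 15 | 91 vs 96% | 91 vs 96% |
| 0.7 | 85% | 17 | 99 vs 99% | 91 vs 94% |
| 0.9 | 95% | 19 | both near 100% | 91 vs 92% |
| 0.95 | 97.5% | 19.5 | both near 100% | 91 vs 91% |

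Repeat runs agree to within about 1 point. With no effect, the change test rejected in 9.4–9.8% of trials and the residual test in 9.5–9.8%, so both keep their level. The largest loss for the residual test under normality was about 0.3 point, at r = 0.95.

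**Step 4: departures from the model, effect 1.0 SD of change.**
- Lognormal data left unlogged, change versus residual rank-sum: 90.0 vs 87.9% at r = 0.9 and 88.8 vs 86.7% at 0.95, a loss of about 2 points. On the log scale the residual test gave 91.9 and 91.1%.
- Heavy tails: the residual rank-sum test lost at most 0.6 to 0.8 point across separate runs.
- ANCOVA does slightly better than residual rank-sum under normality (97.0% at r = 0.5) but is less robust. Against the change rank-sum test it gave 94.6 vs 98.7% (r = 0.9) and 94.4 vs 98.9% (0.95) with heavy tails, and 85.8 vs 89.6% and 84.7 vs 88.7% on unlogged lognormal data. That is a loss of about 4 points.

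**The case against.** The strongest reply is that nothing here is an error. The test is valid, the endpoints are secondary, and this is a pilot. If the 1.0 SD target means the SD of the response being tested, which is the natural reading for blood, the change test has about 91% power at every r and meets the plan's criterion. With 14 to 21 days between samples, r may well be high, and at r of 0.8 to 0.95 the gain on that scale is only 0 to 2 points. All of this stands. It limits the point to a cheap improvement of uncertain size.

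A further reply is that adjustment adds choices of method and scale for ten analytes where the plan has one fixed test. That also stands in part. It is met by naming a single method and fixing one scale per analyte in advance.

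A reader might infer that the plan misses its own 90% criterion. On the level-SD reading, the power of the change test does fall below 90% at r of 0.4 or less (86.9% at 0.4). The documents do not support that conclusion, because they give neither r nor the scale of the SD.

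A reader might also infer from the differing tissue passages that the primary tissue comparison is undefined or unsound. The documents do not support that either. Section C describes tissue taken after surgery. The statistical section defines a pre/post difference for blood but only a tumor-minus-NTU difference for tissue. The secondary objectives attach the two time points to the blood items and not to the tissue item. Neither Proliferation Markers nor section C says that surgical tissue is the sole source. Following the plan as written would give a sound comparison of surgery specimens.

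**Conclusion.** The point holds as an efficiency matter for the ten named blood analytes and merits consideration, no more. The planned test is valid and the stated power is correct. Relative to baseline adjustment, the raw change may waste 35, 25, 15 or 5% of the information at r = 0.3, 0.5, 0.7 or 0.9. This rests on equal SDs at the two visits, a linear relation on the chosen scale, and an r that the documents do not supply. The gain in power could reach about 11 points at r = 0.3 for a 1.0 level-SD effect, and it is negligible at about r = 0.9 and above.

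The tissue passages need only a minor clarification. An analysis adjusted for diagnostic tissue is not recommended: its benefit would depend on an unknown correlation and on unknown biopsy availability.

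**What to change.** 1. For the ten named analytes, regress the surgery value on the pre-study value with both arms pooled, and apply the planned two-sided rank-sum test at 10% alpha to the residuals. Make this the between-arm test.
2. Fix one scale per analyte in the SAP before arm-level data are seen, with logs for skewed analytes. Do not list ANCOVA as an equal alternative.
3. Keep the summaries of change and the within-arm signed-rank tests as planned.
4. State either that the plasma mRNA and miR profiles keep the change test, or that they receive the same adjustment.
5. As a clarification, reconcile the Protocol Summary, Proliferation Markers, section C and the Study Calendar: say what diagnostic tissue is used for, and that the between-arm tissue tests use the surgery specimen.

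The cost is a few sentences and a little programming. No new samples are needed. The residual test needs the same two values per patient as the change test, so the set of analysable patients does not shrink. The price is reliance on a linear baseline model on a suitable scale: up to about 1 point of power lost with heavy tails, and about 2 points on unlogged skewed data at high r.

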## **Dissemination of Data**

The results will be analyzed after the analysis of all the blood and tissue samples. Then the two groups will be compared and the statistical analysis will be performed. The results will be submitted for presentation at national meetings, manuscripts will be written for publication and the data will be used to apply for additional funding from federal agencies including the National Institutes of Health/National Cancer Institute (NIH/NCI).

Official Title: A Randomized Pilot Study to Evaluate the Effects of a Short Course of Metformin versus No Therapy in the Period Prior to Hysterectomy for Grade 1-2 Adenocarcinoma of the Endometrium in Obese Non-Diabetic Women

Protocol - Statistical Analysis Plan, v10 dated 5/24/2016

Data Handling and Recordkeeping

The PI will carefully monitor study procedures to protect the safety of research subjects, the quality of the data and the integrity of the study. The data will be kept in an electronic database in the office of clinical trials at the Winthrop P. Rockefeller Cancer Institute. Only the PI and Co-I, CRAs, regulatory personnel, biostatistician and lab personnel performing the analyses will have access to the data. In the event that a subject fails screening, only the eligibility criteria case report form will be completed.

Monitoring

Medical Monitor: The Medical Monitor, Principal Investigator and study staff will meet quarterly, once the PI has monitored the data, to review safety data (adverse events, serious adverse events and other scientific observations).

Study Monitor: The study will be monitored to ensure that the rights and well-being of human subjects are protected, that the data are accurate, complete and verifiable from source documents and that the trial is conducted in compliance with currently approved protocol/amendments on a quarterly basis.

Statistical Considerations

General approach: For each tissue endpoint, the tumor-NTU difference will be calculated in each patient as the paired difference in values between tumor and adjacent NTU tissue. For each blood endpoint, the endpoint response to treatment will be calculated in each patient as the paired difference between post-study and pre-study values. All data will be summarized by treatment arm as the mean, standard deviation (SD), median, and range, and will be graphed as box plots. Tumor-NTU differences and endpoint responses will be compared against zero via signed-rank test within each treatment arm. Treatment arms will be compared to each other for differences via Wilcoxon rank-sum tests, with additional details provided below. All statistical comparisons will be two-sided, and will employ a 10% alpha to reduce Type II error in this pilot proof-of-concept study.

Analysis plan for tolerability: Meformin-related adverse events will be summarized by type and treatment arm, both as proportions at each grade and as average grades (i.e., mean scores). For each type, the Wilcoxon rank-sum test will be used to compare treatment arms for differences in average grade.

Analysis plan for the IHC-based primary endpoints: The IHC-based primary endpoints will be measured in tissue, and will include markers of proliferation (Ki67, phospho-histone H3, ER α , PR, and hTERT), anti-proliferation and apoptosis (PTEN, KLF9, cleaved caspase-3 and TUNEL staining), and insulin-mediated signalling (total and phosphorylated versions of Akt, Erk1/2, AMPK, and receptors for Insulin, IGF-I, and IGF-

II). Endpoints measured in tumor tissue, adjacent NTU tissue, and tumor-NTU differences will be summarized and graphed as described above. Wilcoxon rank-sum tests will be used to compare endpoints measured in tumor, and likewise endpoints measured in adjacent NTU tissue, for differences between the metformin and no-metformin treatment arms.

Analysis plan for secondary endpoints measured in blood or plasma: The secondary endpoints measured in blood will be the levels of HbA_{1c}, cholesterol, HDL-C, LDL-C, and triglycerides. The secondary endpoints measured in plasma will be the plasma hormone levels (Insulin, IGF-I, IGF-II, leptin, and adiponectin) and the plasma-measured expression levels of mRNAs and miRs. Endpoints measured at pre-study and post-study, and endpoint responses to treatment will be summarized and graphed as described above. Wilcoxon rank-sum tests will be used to compare endpoint responses to treatment for differences between the metformin and no-metformin treatment arms.

Analysis plan for secondary endpoints measured in tissue: The secondary endpoints measured in tissue will be the expression levels of mRNAs and miRs. Endpoints measured in tumor tissue, adjacent NTU tissue, and tumor-NTU differences will be summarized and graphed as described above. Wilcoxon rank-sum tests will be used to compare endpoints measured in tumor, and likewise endpoints measured in adjacent NTU tissue, for differences between the metformin and no-metformin treatment arms.

Sample Size and Power: There will be 20 subjects on each treatment arm, yielding a total of 40 subjects. The two-sided Wilcoxon rank-sum test will be used at 10% alpha to compare all endpoints and endpoint responses for differences between the metformin arm and the no-metformin arm. This study will be considered sufficiently powered to meet research objectives if the Wilcoxon rank-sum test has >90% power at 10% alpha to detect a treatment-arm difference of 1.0 SDs or more. Statistical power of the Wilcoxon rank-sum test was calculated using the 2-sample t-test module of PASS 2011 by selecting options corresponding to the worst-case scenario of underlying normal distributions with unknown SDs. Under this worst case scenario, 20 subjects per treatment arm (for a total of 40 subjects) give the two-sided Wilcoxon rank-sum test 91.6% power at 10% alpha to detect a difference of 1.0 SDs between the metformin and no-metformin arms, thereby establishing that this study is sufficiently powered to meet research objectives.

Dissemination of Data

The results will be analyzed after the analysis of all the blood and tissue samples. Then the two groups will be compared and the statistical analysis will be performed. The results will be submitted for presentation at national meetings, manuscripts will be written for publication and the data will be used to apply for additional funding from federal agencies including the National Institutes of Health/National Cancer Institute (NIH/NCI).
